4.4.3 *Safety Pharmacology and Toxicity Studies*

Details of the preclinical safety and toxicity studies of YKP3089 can be found in the Investigator's Brochure. The most common AEs in preclinical studies of YKP3089 involved the central nervous system (CNS). The incidence and severity of these signs increased with

increasing dose, and the signs resolved during the recovery periods. In mice and rats, the median neurotoxic dose of YKP3089 was calculated to be between 50 and 350 mg/kg, a dose greater than that required to elicit antiepileptic effects (ie, 3 to 30 mg/kg).

In a special neurotoxicity safety pharmacology study in cynomolgus monkeys, no evidence of drug-induced epileptic convulsions was observed at 30, 40, or 60 mg/kg/day administered for 4 days. Severe toxicity was noted at 40 and 60 mg/kg/day requiring euthanasia of 1 animal and halting of dosing for 3 others before the end of the scheduled 4 days of administration. At 60 mg/kg/day, myoclonus and/or intention tremors were noted in 2 of 6 animals.

YKP3089 had no effect on cardiac (ECG) or circulatory function in monkeys, as measured by telemetry. Nor was there evidence of cardiotoxicity in studies of rats or monkeys. YKP3089 at doses up to 30 mg/kg had no effect on pulmonary function or cause bronchoconstriction.

Reproductive toxicity studies showed adverse effects on reproductive performance when the dosage of YKP3089 was high enough to induce maternal toxicity, as evidenced by decreased food consumption and decreased body weight. However, there was no evidence of teratogenicity.

The results of standard genotoxicity studies of YKP3089 were negative. No tests of carcinogenicity have been conducted.

4.4.4 *Clinical Safety*

Approximately 400 human subjects have been exposed to YKP3089 in 15 completed (13 Phase 1, 1 proof-of-concept) and 1 Phase 2a).

In a multiple ascending dose study in healthy volunteers, when doses of 250 to 300 mg once daily were given from Day 1, somnolence, dizziness, and decreases in mean systolic blood pressure have been seen, but no serious AEs have been reported. Horizontal nystagmus, ataxia, and gait disturbance have also been observed in normal volunteers receiving 250 and 300 mg once daily. These reactions resolved after YKP3089 was discontinued at the end of the study. At 300 mg once daily, a mean shortening of the QT_{CF} interval of 10 to 15 msec was observed.

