The initial target dose for the open-label extension will be 300 mg/day. However, if a subject is not tolerating the 300 mg/day dose, YKP3089 dose may be reduced to a minimum of 50 mg/day. If the investigator feels that a subject requires a dose that is higher than 300 mg/day, the dose can be increased to a maximum of 400 mg/day once the target dose of 300 mg/day was reached. The dose adjustments may occur in weekly increments of 100-mg/day or 50-mg/day. However, the rate of change may be more rapid or slow as clinically indicated. No dose reductions are permitted if the subject is taking 50 mg/day YKP3089. If 50 mg/day YKP3089 is not tolerated, the subject will withdraw from the study. Monotherapy with YKP3089 will not be allowed. The investigator may add, remove, or adjust the dosage of concomitant AEDs, as clinically indicated. In the event of poor tolerability, the investigator may instruct the subject to take the dose of study medication in the evening or divide the total daily dose into 2 doses. Subjects will follow the schedule of study visits and assessments detailed in [Table 2](#). After 12 months of participation in the open-label extension phase, subjects will be re-evaluated. Those who are benefiting from treatment with YKP3089 may continue use of the drug at the discretion of the investigator, until development is stopped by SK Life Science Inc or the product is approved for marketing, or anytime at the discretion of SK Life Science Inc.

6.1.4.3 *Study Drug Taper: Subjects Leaving the Open-Label Extension*

Subjects who are withdrawn from the open-label extension study will taper YKP3089 according to the schedule described in [Table 6](#), unless for safety reasons the investigator judges it necessary to discontinue study drug immediately. The investigator is encouraged to discuss the tolerability criteria with the Sponsor or its designee.

Table 6. Study Drug Taper Schedule for Subjects Completing Open-Label Extension

Final open-label dose of YKP3089 (mg/day)	YKP3089 Dose During Taper (mg/day)		
	Week 1	Week 2	Week 3
50 or 100	None		
150 or 200	100	None	None
250 or 300	200	100	None
350 or 400	300	200	100

The final visit will take place 14 days after the subject's last dose, following taper and discontinuation of YKP3089; at any time during the open-label treatment; or after 12 months of open-label treatment if there is no additional treatment beyond that point.

6.1.5 *Dose Adjustments of Study Drug and Concomitant AEDs*

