11.3.3 Analysis of Electrocardiograms

All ECG results will be listed on a by-subject basis. ECG parameters consist of heart rate (bpm), PR interval (msec), RR interval (msec), QRS-complex (msec), uncorrected QT interval (msec), and QTcF interval (msec). Individual ECG values (parameters) will be listed by subject and visit. Baseline measurement is defined as the last available measurement prior to dosing in double-blind period.

For summary tables, the following rules will be applied to derive a single value corresponding for this visit:

- For all numerical values, the average of the 3 measurements will be computed
- For qualitative values (normal / abnormal):

SAP-OLE Version Final_15May2021 Page 30 of 43

- If 2 or more results are "abnormal", visit 3 derived results will be "abnormal" (this rule applies for subjects with 3 or 2 measurements)
- Otherwise, visit 3 derived results will be "normal".

For subjects with only one measurement collected at Visit 1 (DB baseline),

the collected value will be used as baseline value for summary results.

For the OLE-SE analysis population the following summary tables will be generated for the ECG data:

- Summary statistics (n, mean, standard deviation, median, minimum, and maximum) of the baseline value, the value at each scheduled postbaseline evaluation, and the corresponding change from baseline for each continuous ECG parameter,
- Count and percentage of subjects with QTcF absolute value > 450 msec, >480 msec, >500 msec, <360 msec, <340 msec, <320 msec, and <300 msec at each scheduled post-baseline evaluation,
- Count and percentage of subjects with a mean change from baseline in QTcF intervals >30 msec, >60 msec >90 msec, <30 msec, <60 msec, and <90 msec at each scheduled post-baseline evaluation,
- Count and percentage of subjects with absolute heart rate > 100 bpm at each scheduled post-baseline evaluation,
- Count and percentage of subjects with heart rate change from baseline >10 bpm, >20 bpm, and >30 bpm at each scheduled post-baseline evaluation,

For these summary tables, results will be reported using visit windows as defined in Appendix 14.1.

ECG results during OLE will be listed by subject.

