14 APPENDIX 2: VISIT WINDOWS

14.1 ECG

The following visit windows will be applied for reporting **ECG** results open-label extension results:

Analysis Timepoint	C017 OLE	
	Target Study Day [1]	Window [2]
		Study Days
Baseline	1	<= 1
Start of OLE [3] – Visit 9	127	>= 113 to <= 141
Visit 12	155	>=142 to <= 323
Visit 16	491	>=324 to <=659
Visit 20	827	>=660 to <= 995
Visit 24	1163	>=996 to <=1306
Visit 28	1499	>=1307 to <=1642
Visit 32	1835	>=1643 to <= 2003
Visit 36	2171	>= 2004 to <=2339
Visit 40	2507	>= 2340 to <= 2675
Visit 44 [4]	2843	>=2676

OLE=Open-label Extension

^[1] Relative to the date of the first dose of study drug. For example, Day 1 = the date of the first dose of study drug.

^[2] The study days evaluated for windows of visits during treatment period are on or prior to the last dose day.

^[3] This window should include the study day when the first dose of OLE study medication was given.

^[4] Expected timepoint C017 OLE.

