14.2 Clinical Laboratory Assessments

The following visit windows will be applied for reporting **clinical laboratory** open-label extension results:

Analysis Timepoint	C017 OLE	
I IIII Openii	Target Study Day [1]	Window [2]
		Study Days
Baseline	1	<= 1
Start of OLE [3] – Visit 9	127	>= 113 to <= 141
Visit 12	155	>=142 to <= 239
Visit 14	323	>=240 to <=407
Visit 16	491	>=408 to <= 575
Visit 18	659	>=576 to <=743
Visit 20	827	>=744 to <=911
Visit 22	995	>=912 to <=1079
Visit 24	1163	>= 1080 to <=1247
Visit 26	1331	>= 1248 to <=1415
Visit 28	1499	>=1416 to <=1583
Visit 30	1667	>=1584 to <=1751
Visit 32	1835	>=1752 to <=1919
Visit 34	2003	>=1920 to <=2087
Visit 36	2171	>=2088 to <=2255
Visit 38	2339	>=2256 to <=2423
Visit 40	2507	>=2424 to <=2591

Visit 42	2675	>=2592 to <=2756
Visit 44 [4]	2843	>=2760

OLE=Open-label Extension

- [1] Relative to the date of the first dose of study drug. For example, Day 1 = the date of the first dose of study drug.
- [2] The study days evaluated for windows of visits during treatment period are on or prior to the last dose day.
- [3] This window should include the study day when the first dose of OLE study medication was given.
- [4] Expected timepoint C017 OLE.

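### Open-label SAP: three visit-window limits are wrong, the QTcF change categories are printed without minus signs, and the ECG baseline wording conflicts

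*SAP*

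**What the plan says.** **Windows.** SAP 14.1 assigns ECGs to visits by study day. Visit 24 (target Day 1163) runs from Day 996 to 1306, Visit 28 (target 1499) is ">=1307 to <=1642", and Visit 32 (target 1835) runs from 1643 to 2003. In SAP 14.2, lab Visit 42 (target 2675) is ">=2592 to <=2756" and Visit 44 (target 2843) opens at Day 2760.

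**QTcF categories.** SAP 11.3.3 counts subjects with a "mean change from baseline in QTcF intervals >30 msec, >60 msec >90 msec, <30 msec, <60 msec, and <90 msec". The same section counts "QTcF absolute value > 450 msec, >480 msec, >500 msec, <360 msec, <340 msec, <320 msec, and <300 msec", summarises "the corresponding change from baseline for each continuous ECG parameter" (mean, SD, median, minimum, maximum), and lists the open-label ECGs by subject.

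**Baseline.** SAP 11.3.3 takes the last ECG before double-blind dosing as baseline. It then averages three readings for numerical values, applies a two-or-more-abnormal rule whose result is labelled visit 3, and adds a fallback that begins "For subjects with only one measurement collected at Visit 1 (DB baseline". Protocol Table 1 marks triplicate recording at Visit 1 only. Protocol 9.1.3 asks for a standard ECG at Visit 3. Table 1 heads Visit 3 as the safety baseline, and its footnote l gives that role to the Day 1 values.

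**Background.** Protocol 4.4.4 reports that, in healthy volunteers on 300 mg once daily, a mean shortening of the QTcF "interval of 10 to 15 msec was observed". Protocol 6.1.4.2 states: "The initial target dose for the open-label extension will be 300 mg/day".

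**The concern.** The two odd ECG limits move results to a visit whose target day is farther away, and the lab table has a hole between two windows. A programmer who follows the tables literally will reproduce both faults.

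The QTcF change rows matter because shortening is the QT effect that the protocol reports, at the dose that is also the open-label target. The low absolute cut-offs in the same section suggest that the second set of change cut-offs was meant for shortening. Without minus signs, those rows count subjects who merely did not lengthen by the stated amount.

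The baseline wording reaches furthest. Every ECG change from baseline, including the QTcF and heart-rate categories, depends on whether the Visit 3 reading or the Visit 1 mean is used.

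**Working it through.** **1. The pattern behind the windows.** The SAP does not state a rule, but its tables follow one: upper limit = (target + next target)/2, and next lower limit = upper limit + 1. For example, (827 + 1163)/2 = 995, the stated end of ECG Visit 20. This reproduces 7 of 9 limits between adjacent visits for ECG, 16 of 17 for labs and 34 of 34 for vital signs (SAP 14.3). The gap from Day 1 to Day 113 after Baseline is left out of the count because it is not a boundary between open-label visits.

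The three exceptions:

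| Limit | Midpoint | Stated | Difference |
|---|---|---|---|
| ECG Visit 24 | (1163 + 1499)/2 = 1331 | 1306 | 25 days early |
| ECG Visit 28 | (1499 + 1835)/2 = 1667 | 1642 | 25 days early |
| Lab Visit 42 | (2675 + 2843)/2 = 2759 | 2756 | 3 days early; next window starts at 2760 |

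ECG Days 1307-1331 therefore go to Visit 28, and Days 1643-1667 to Visit 32. On the last day of each range (1331, 1667) the two targets are equally near; on the others the earlier target is nearer. The windows for ECG Visits 24, 28 and 32 are 311, 336 and 361 days long; under the midpoint rule each would be 336. The ECG windows are contiguous, so no ECG day is left out. Lab Days 2757, 2758 and 2759 belong to no window.

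**2. Which results are touched.** The protocol allows ±7 days for these visits (9.3). ECGs on schedule fall on Days 1156-1170, 1492-1506 and 1828-1842. Labs on schedule fall on Days 2668-2682 and 2836-2850. None lies in an affected range. Counting calendar years from Day 491 instead gives ECGs at about Days 1222, 1587 and 1952 and labs at about Days 2682 and 2865, which are also clear. Days 1331, 1667 and 2759 are the SAP 14.3 targets for Visits 26, 30 and 43, when no ECG (26, 30) or lab (43) is due. An extra ECG or lab taken at one of those visits is the kind of result affected.

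**3. QTcF change rows.** A change <30 is the complement of >30, apart from exactly 30. To size this, take the change as normal with mean m and SD s, so P(change < c) = Φ((c - m)/s). The protocol gives m = -10 to -15 msec. The documents give no SD; I assume 10 to 20 msec.

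| Row | No effect (m = 0) | m = -10 to -15 |
|---|---|---|
| < 30 | Φ(30/20) = 93.3% to Φ(30/10) = 99.9% | Φ(40/20) = 97.7% to Φ(45/10) = 100% |
| < -30 | Φ(-30/10) = 0.1% to Φ(-30/20) = 6.7% | Φ(-20/10) = 2.3% to Φ(-15/20) = 22.7% |

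The <60 and <90 rows hold 99.9% to 100% in every case. As printed, the three rows barely differ between a drug that shortens QTcF and one that does not.

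**4. Baseline, side by side.** Last value before dosing points, on schedule, to Visit 3, which has one ECG. The average of three readings points to Visit 1, the only visit scheduled for triplicates. The fallback labels Visit 1 the double-blind baseline, while the normal/abnormal rule names visit 3. The sentence introducing these rules speaks of this visit without saying which one it means. These statements do not describe a single rule.

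**The case against.** **The sign may not be missing.** The exposure formulas in SAP 8.5 also appear without their minus signs, so conversion may have removed them here too. The table templates are a separate document. Against that, the percent-change formula in SAP 9 kept its minus. The question is open, and a reader who takes the sign as a proven error goes further than the documents allow.

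**Shortening would still be visible.** A reader might infer that the ECG plan cannot show QT shortening at all. The documents do not support that. The absolute low-QTcF counts, the continuous change summaries with their minimum, and the listings would all show it. Only the categorical change table fails.

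**The window slips are small.** The midpoint rule is inferred, no ECG is lost, the unplaced labs stay in the listings, and scheduled visits are untouched. The open-label analyses are descriptive (SAP 11.1). All of this stands. It limits the consequence but does not make the limits right: nothing explains two 25-day departures or a three-day hole.

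**The baseline wording may be only loose.** The averaging bullet names no visit; visit 3 appears only in the normal/abnormal rule. That is correct, but the section still points to two different visits as baseline.

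**The assumed effect may not apply.** The 10 to 15 msec comes from healthy volunteers, and Protocol 4.6 reports no significant electrocardiographic abnormalities in the Phase 2a patients. This bears on the percentages in step 3, but not on the fact that <30 is the complement of >30.

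**Conclusion.** The point holds as a set of specification errors to correct before the open-label tables are run. Two ECG limits are 25 days early, and three lab days have no window. Both follow from the printed numbers and need no assumption beyond the pattern that the rest of the tables show. A reader might infer that scheduled results are widely misfiled or that ECGs disappear. The documents support neither: only off-schedule, unscheduled or early-termination results can be affected, and only labs lose a place in the summaries and shift tables.

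The QTcF change categories are uninformative about shortening as printed, subject to a check of the source. The percentages rest on an assumed SD of 10 to 20 msec and a normal distribution; the conclusion does not.

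The baseline conflict is real and affects every ECG change value. It might seem to call for a baseline that pools the Visit 1 and Visit 3 readings, but that would be a new definition found in neither document.

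**What to change.** - **SAP 14.1:** set ECG Visit 24 = Days 996-1331, Visit 28 = 1332-1667 and Visit 32 = 1668-2003.
- **SAP 14.2:** set lab Visit 42 = Days 2592-2759.
- **SAP 11.3.3, categories:** check the cut-offs against the source file. If the sign is missing there too, write < -30, < -60 and < -90 msec.
- **SAP 11.3.3, baseline:** reconcile the wording to one rule that agrees with the protocol's Day 1 safety baseline and with the double-blind SAP (cited in SAP 6 but not among these documents). State which visit the three-reading and single-reading rules apply to. Do not add a pooled definition.

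The cost is a short text revision, which SAP 4 allows before the open-label database lock, with matching changes to the programs. No new data are needed.

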11.3.4 Analysis of Vital Signs

All Vital Signs will be listed on a by-subject basis. Baseline measurement is defined as the last available measurement prior to dosing in double-blind period. Vital signs result during open-label phase will be summarized by OLE treatment groups. For these summary tables, results will be reported using visit windows as defined in Appendix 14.3.

11.3.5 Analysis of Physical and Neurologic Examination Results

Physical and neurological examination results during OLE will be included in bysubject listings only.

11.3.6 Columbia Suicide Symptoms and Signs Rating Scale (CSSRS)

At each visit during OLE, C-SSRS responses will be mapped into Columbia-Classification Algorithm of Suicide Assessment events on as follows:

- Complete suicide = as captured in the safety database (adverse events and/or reason for discontinuation)
- Suicide attempt: "Yes" on "Actual attempt" question
- Preparatory acts towards imminent suicidal behavior: "Yes" on any of the following
 - "Aborted attempt", or
 - "Interrupted attempt", or
 - "Preparatory acts or behavior".
- Suicidal ideation: "Yes" on any of the following:
 - "Wish to be dead", or
 - "Non-specific active suicidal thoughts", or
 - "Active suicidal ideation with any methods (not plan) without intent to act", or
 - "Active suicidal ideation with some intent to act without specific plan", or
 - "Active suicidal ideation with specific plan or intent".

For OLE, C-SSRS results will be included in by-subject listings only.

12 GENERAL PROGRAMMING SPECIFICATIONS

Computer generated tables described in this analysis plan will adhere to the following specifications.

(a) The estimated mean and median for a set of values will be reported to one more decimal place than the raw (observed) data and rounded appropriately. The standard errors (or standard deviations [SD]) will be reported to two additional decimal places than the raw (observed) data and rounded appropriately. For example, for age (with raw data in whole years):

N XX

Mean (SD) XX.X (X.XX)

Median XX.X Range XX-XX

- (b) Data in columns of a table will be formatted as follows:
 - i. Alphanumeric values will be left-justified (in mixed and upperand lower-case)
 - ii. Whole numbers (e.g., counts) will be right justified
 - iii. Numbers containing fractional portions will be decimal aligned
- (c) All fractional numeric values will be reported with a zero to the left of the decimal point (e.g., 0.12-0.3).
- (d) Percents will be reported to one decimal place.
- (e) Dates will be reported in SAS DATE9. format (e.g., 29MAR2007). Missing portions of dates should be represented on subject listings as dashes (--MAR2007). Dates that are missing because they are not applicable for the subject should be listed as "N/A", unless otherwise specified.
- (f) The table should be typed in Arial 10-point font. The table title should be typed in Bold Initial Caps, Arial 10-point font, beginning with the word Table X, Title.
- (g) Header (or footer) information for all tables, figures, and listings (TFLs) will include the protocol number, table status (draft or final) and the date and time the table was created.
- (h) Any TFLs generated prior to database lock or completion of TFL validation will be marked "Draft".

13 APPENDIX 1: PROTOCOL DEVIATIONS

The following are predefined protocol deviations:

Code	Description	Comment
Α	Entrance criteria not met	
A1	Inclusion criteria not met	
A1.1	Male or Female, 18 to 70 years of age inclusive.	Inclusion criterion 1
A1.2	Weight at least 40 kg.	Inclusion criterion 2
A1.3	During the 8-week baseline period, subjects must have at least 8 partial seizures including only simple partial seizures with motor component, complex partial seizures, or secondarily generalized seizures without a seizure-free interval of greater than 25 days any time during the 8 weeks baseline. Subjects must have at least 3 of these partial seizures during each of the two consecutive 4-week segments of the baseline period	Inclusion criterion 6
A2	Important exclusion criteria met	
A2.1	History of serious systemic disease, including hepatic insufficiency, renal insufficiency, a malignant neoplasm, any disorder in which prognosis for survival is less than 3 months, or any disorder which in the judgment of the investigator will place the subject at excessive risk by participation in a controlled trial.	Exclusion criterion 1
A2.2	A history of nonepileptic or psychogenic seizures	Exclusion criterion 2
A2.3	Presence of only nonmotor simple partial seizures or primary generalized epilepsies).	Exclusion criterion 3
A2.4	Presence or previous history of Lennox-Gastaut syndrome.	Exclusion criterion 5
A2.5	Pregnancy or lactation	Exclusion criterion 6

A2.6	Any clinically significant laboratory abnormality that in the opinion of the Investigator would exclude the subject from the study	Exclusion criterion 8
A2.7	Evidence of significant active hepatic disease. Liver transaminases (AST or ALT) above twice the upper limit of normal or total or direct bilirubin not within normal limits	Exclusion criterion 9
A2.8	An active CNS infection, demyelinating disease, degenerative neurologic disease, or any CNS disease deemed to be progressive during the course of the study that may confound the interpretation of the study results	Exclusion criterion 10
A2.9	Presence of psychotic disorders and/or unstable recurrent affective disorders evident by use of antipsychotics; presence or recent history (within 6 months) of major depressive episode	Exclusion criterion 12
A2.5	Use of intermittent rescue benzodiazepines more than once per month (1 to 2 doses in a 24-hour period is considered 1 rescue) in the 1 month period prior to Visit 1	Exclusion criterion 13
A2.6	History of alcoholism, drug abuse, or drug addiction within the past 2 years	Exclusion criterion 14
A2.7	Current use of felbamate with less than 18 months of continuous exposure	Exclusion criterion 15
A2.8	Current use of diazepam, phenytoin, phenobarbital, or metabolites of these drugs (within 1 month of Visit 1)	Exclusion criterion 16
A2.9	Current or recent (within the past year) use of vigabatrin. Subjects with a prior history of treatment with vigabatrin must have documentation showing no evidence of a vigabatrin associated clinically significant abnormality in a visual perimetry test	Exclusion criterion 17
A2.10	History of status epilepticus within 3 months of Visit 1	Exclusion criterion 18
A2.11	History of 1 serious drug-induced hypersensitivity reaction (including but not limited to Stevens Johnson syndrome, toxic epidermal necrolysis, drug reaction	Exclusion criterion 19

C1	Incorrect medication dose taken	
C	first study related activity Trial medication & randomization	
B1 B2	Informed consent not available Informed consent signed and dated after	
В	Informed consent	
A2.20	Presence of congenital short QT syndrome	Exclusion criterion 30
A2.19	History of positive antibody/antigen test for hepatitis B, hepatitis C, or HIV	Exclusion criterion 29
A2.18	Current use of any of the following medications: clopidogrel, fluvoxamine, amitriptyline, clomipramine, bupropion, methadone, ifosfamide, cyclophosphamide, efavirenz, or natural progesterone (within 1 month of Visit 1	Exclusion criterion 28
A2.17	More than 1 lifetime suicide attempt	Exclusion criterion 26
A2.16	A "yes" answer to Question 1 or 2 of the C-SSRS (Baseline/Screening version) Ideation Section in the past 6 months or a "yes" answer to any of the Suicidal Behavior Questions in the past 2 years.	Exclusion criterion 25
A2.15	Platelet counts lower than 80,000/µL in subjects treated with VPA	Exclusion criterion 24
A2.13	Absolute neutrophil count less than 1500/µL Clinical or ECG evidence of serious cardiac disease, including ischemic heart disease, uncontrolled heart failure, and major arrhythmias, or relevant replicated changes in QT intervals (QTc _F less than 340 msec or greater than 450 msec in males and greater than 470 msec in females)	Exclusion criterion 22 Exclusion criterion 23
AO 40	as calculated by the Cockcroft-Gault equation	Evaluaion oritorian 22
A2.12	with eosinophilia and systemic symptoms) or any drug-related rash requiring hospitalization Creatinine clearance less than 50 mL/min,	Exclusion criterion 21

C2	Randomization not followed	
C3	Non-compliance	e.g., compliance rate < 80%
D	Concomitant medication	
D1	Use of prohibited concomitant medications	

